#### AIM 4 (EFFECTIVENESS)

Parent/caregiver and child participants in Aim 4 will engage in assessments scheduled every six months over approximately 3.25 years or until the study ends. In addition, participants randomized to the FCU-DHH condition will be offered the FCU-DHH intervention annually (described below). Participants randomized to the treatment-as-usual (TAU) control condition will complete assessments only throughout the course of the study. Research staff conducting data collection will be blinded to participants' random assignment (i.e., FCU-DHH vs. TAU).

(1) Procedures for Parent/Caregiver and Child Participants: In Aim 4, the primary parent/caregiver participant will complete the baseline assessments of parent- and child-level constructs either online via REDCap survey or by mailed paper forms (see Form M and description below). All parent/caregiver participants will also be offered the option to complete assessments with research staff over the phone to alleviate literacy or comprehension concerns. Four standardized videotaped parent/child tasks and a brief parent interview about how the child can hear in various situations will also be completed at baseline, with video captured remotely by HIPAA-compliant videoconferencing software. If parents do not have the capability to connect to videoconference sessions with equipment they own, the research staff will arrange a way to deliver equipment to the family (e.g., drop off equipment while waiting outside, or deliver by certified mail). For participants enrolled after the 3/2/2023 IRB modification/approval (in which participants will not complete any measures past 18-month assessments), the child participant will also participate in baseline speech, language, and hearing assessments with the trained data collector via HIPAA-compliant videoconferencing software (see description of measures, below, as well as Form M). Data collection for the parent/caregiver and/or the child will be separated into more than one session as needed to

prevent fatigue. No data collection will occur unless informed consent has been documented by REDCap or by a mailed copy of a signed paper consent form. Upon completion of baseline data collection, participants will be notified by mailed or emailed letter (according to the parent's preference) of their next steps in the study, depending on whether they were randomized to the FCU-DHH or TAU condition.

Participants randomized to the TAU control condition (n=53 dyads) will receive treatment as usual throughout Aim 4 (i.e., for most, this involves hearing healthcare appointments approximately every 6 months with their practice's providers, which may include nurses, care coordinators, ENT physicians, audiologists, and social workers).

Participants randomized to the intervention condition (FCU-DHH) (n=72 dyads) will be scheduled for their first FCU-DHH session with a trained parent coach within 2 weeks of completing the baseline assessment. Each FCU-DHH session will be delivered by a trained parent coach via videoconference or telephone. Between the first and second FCU-DHH sessions, the parent/caregiver will complete a FCU questionnaire (either online via REDCap survey, by mailed paper forms, or by telephone) that helps the parent coach understand more about the parent and child in the study and about their family context. Additional caregivers may also complete questionnaires if they have provided their consent to participate in the study. These assessments are part of the FCU intervention and will be used to populate the Feedback Form given to families by the parent coach in the second FCU session. The FCU questionnaire will not be included as sources of data for analysis of the study by researchers. If item responses are available from the parent/caregiver's baseline or annual assessments, they will not be re-asked in order to reduce participant burden (e.g., the PARYC items are part of the FCU questionnaire and will not be re-asked of primary participants; additional caregivers will still need to complete these items). The parent/caregiver will subsequently engage in up to 6 Family Check-Up sessions total within the next 4-5 months (total possible = 6 sessions per year). FCU-DHH sessions include one 60-minute assessment session (interview, questionnaires), one 45-minute feedback and motivational interviewing session, and up to four 60-minute skills-training sessions (focused on positive parenting skills such as focused praise, positive reinforcement, effective limit-setting, using consistent consequences).

Parents in either the control or intervention conditions can be referred to additional services within their state that support families with DHH children. For example, a family in either the control or intervention group who expresses a need for services such as social connections with other families of DHH children or a need for assistance in developing an Individualized Education Plan for their child can be referred to their state's Hands & Voices chapter.

Six months after baseline, each primary parent/caregiver participant (in both the TAU and FCU-DHH conditions) will complete follow-up assessments either online via REDCap survey, by mailed paper forms, or by telephone with trained research staff (see Form M and description below). There are no child-level measures administered at the six-month assessments.

Twelve months after baseline, all primary parent/caregiver participants (in both the TAU and FCU-DHH conditions) will complete the one-year follow-up assessments of parent- and child-level constructs either online via REDCap survey, by mailed paper forms, or by telephone with trained research staff (see Form M and description below). Procedures will be identical to those described at baseline; the child's speech, language, and hearing assessments, the parent/child videotaped tasks, and the brief parent interview will be repeated and recorded by HIPAA-compliant videoconferencing software. Parents will repeat the "annual" questionnaires.

Within two weeks of completing the one-year assessment, parent/caregiver participants randomized to the FCU-DHH condition will attend their second round of FCU-DHH sessions, delivered remotely by the trained parent coach via videoconference or telephone. The remaining sessions (up to 6 total) will be delivered within the next 4-5 months. Identical procedures as described at baseline will be conducted with this group. TAU participants will continue to receive treatment as usual.

Eighteen months after baseline, all primary parent/caregiver participants will complete follow-up assessments either online via REDCap survey, by mailed paper forms, or by telephone with trained research staff (see Form M and description below). There are no child-level measures administered at the eighteen-month assessments.

This pattern will continue (annual assessment for all participants + FCU-DHH sessions for FCU-DHH participants only, follow-up six months later for all participants) up to a maximum of 36 months after baseline, or until the study ends (participants enrolling after the 3/2/2023 IRB modification/approval are anticipated to end participation after the 18-month assessment). All data collection will occur remotely. This includes full (i.e. "annual") parent and child assessments at baseline (including child assessments of speech, language, and hearing for participants enrolled after the 3/2/2023 IRB modification/approval), 12-month, 24-month and 36-month follow-ups for all participants; reduced (i.e., "mid-year") parent-only assessments at 6-month, 18-month, 30-month follow-ups for all participants; and FCU-DHH sessions for only FCU-DHH participants following the baseline, 12-month, and 24-month assessments). All parents/caregivers will be compensated \$75 following the baseline assessments before 3/2/2023 (which do not include child language measures); \$100 for baseline assessments after 3/2/2023 (including child language measures) and each annual assessment, and \$50 for completing each mid-year assessment. With parental permission, each child will be allowed to select a small age-appropriate toy (stuffed animal, book, puzzle, etc.) following their participation in annual assessments to acknowledge their contribution to the study. No compensation will be provided for participation in the FCU-DHH sessions. This strategy is intended to make the intervention itself as similar as possible to what it would be if offered outside of a research protocol. At the completion of the study, Aim 4 parent participants will receive an additional payment of \$100 if all 7 sets of research assessments are completed, an additional \$75 if 6 sets of assessments are completed, an additional \$50 if 5 sets of assessments are completed, and an additional \$25 if 4 sets of assessments are completed. These amounts are intended to compensate parents for their long-term participation and keep parents engaged even if some assessments are missed.

Description of parent measures: Data collection appointments will be scheduled with each parent-child dyad, on annual and semi-annual basis, as detailed in Form M. All parent/caregiver participants will complete baseline and annual assessments of parent- and child-level constructs, including: a brief sociodemographic background questionnaire also addressing prior healthcare use, child behavior therapy use, and HA/CI adherence (10 minutes); the 100-item CBCL Ages 1.5-5 or the 113-item CBCL Ages 6-18 (15

minutes); the 24-item PARYC (10 minutes); the 19-item PSCS (5 minutes); the 21-item BDI-II (5 minutes); the 25-item PMI (10 minutes); and the MacArthur Bates Words & Sentences form (20 minutes) or the MacArthur Bates Words & Gestures form (20 minutes) for children who do not yet produce 10 or more spoken words. Parents will also participate in a structured interview with the data collector to complete the Meaningful Auditory Integration Scale (MAIS); these assessments will be recorded and independently scored by research staff. Parents and children will complete four standardized Family Interaction Tasks (FIT) at baseline and annual assessments which will be videotaped and coded by two observers using (1) the DPICS coding system to provide an additional objective measure of parenting behaviors, and (2) the Systematic Analysis of Language transcripts (SALT) system for assessment of child language production. For families in the FCU-DHH condition, the FIT videos will also be used by parent coaches in feedback sessions. To increase retention during the study, we will also ask parent participants to complete a "Locator Information" form during baseline and annual assessments. The form lists alternative methods that parents agree can be used to locate them if their primary contact information changes or becomes disconnected during the study. During the initial informed consent process, the participant will indicate whether or not they choose to provide this information via an initialed checkbox on the consent document. If yes, either: a) the online survey will be programmed to display the Locator Form questions; b) the data collector will provide the Locator Information form in the mailed packet; or c) the data collector will ask for that information in a phone call. Any data received by mail will be entered into and stored in REDCap, which will be consulted to determine whether or not to provide copies of the Locator Information Form at follow-up assessments. Both the informed consent document and the text at the top of the locator form emphasize that completing the form is optional. If a research staff member uses this form to locate a participant by contacting a relative/friend listed by the participant, care will be taken to only indicate that we are trying to locate the individual in relation to a study. There will be no disclosure of the nature of the study, and therefore, no disclosure of the child's hearing loss.

At each six-month follow-up assessment (i.e., 6 months, 18 months, 30 months), a subset of these parent measures will be repeated, and the FCU-DHH participants will also complete the Therapy Attitude Inventory (TAI; satisfaction measure; 5 minutes). Parent-report language measures will not be administered at the six-month follow-up assessments to reduce participant burden (i.e., MacArthur-Bates, MAIS). There are also no videotaped FIT tasks at six-month follow-up assessments.

Description of child measures: At annual (12-month, 24-month, 36-month, and baseline for participants recruited after 3/2/2023) assessments, we will administer several key measures of child language development outcomes directly to children: the Ling sounds test (2 minutes); the CELF Preschool-3 (ages 3-6) or the CELF-5 (age 7 years and older; 30 minutes - different subtests used for children 7-8 years vs children 9 years and older); the PPVT-5 (15 minutes); and the BIT (5 minutes). The language assessment will be conducted by Zoom videoconferencing and will be recorded to assist in scoring the assessments per their established protocols. Children will participate in videotaped FIT tasks alongside their parent(s), as described above. Language measures will not be administered at the six-month follow-up assessments (i.e., 6-month, 18-month, 30-month).

Additionally, FCU-DHH participants will complete a 20-item set of questions that assesses their satisfaction with their interventionist (SWI - 5 minutes to complete). Each FCU-DHH participant will answer the SWI questions at the assessment timepoint that most closely aligns with the end of their involvement in the study (e.g., participants who enrolled in 2021 will complete these questions at their 36-month assessment; those who enrolled in 2023 will complete these questions at their 18-month assessment because study funding ends in May 2025). In comparison, the TAI assesses satisfaction with the intervention (not the interventionist) and is repeated at 6-month, 18-month, and 30-month assessments.

For all participants, the battery of measures (see Form M) is written at an 8th-grade reading level or below. Data collectors will be trained by the investigators ([name] for sociodemographic and behavioral measures; [name] for speech and language measures) in standardized protocols for administering these measures.

With authorization from the parent/caregiver's signed informed consent document, as well as any other release forms requested by the hearing healthcare practice, OCSHCN and other participating hearing healthcare practices will provide authorized protected health information from medical records to the UK research staff via encrypted email or other means of HIPAA-compliant transfer. A secure REDCap survey will be offered for clinics to use to enter medical information directly, if preferred. Requested data from medical records will include history of prematurity; age of child; type and severity of hearing loss; etiology of hearing loss; family history of hearing loss; other medical or developmental conditions; medical management and surgical history for hearing loss; stability of hearing loss (stable or progressive); age of diagnosis; age of amplification and/or implantation; average daily duration of HA/CI use from data logging technology, if available; and speech therapy history. No data collection from hearing healthcare practices will occur unless written informed consent, HIPAA authorization, and practice-required release forms have been obtained.

Aim 4 data analyses: To make trial arm (FCU-DHH vs. TAU) comparisons, we will utilize linear mixed modeling. In the models, we will utilize random effects corresponding to the interventionists, thus accounting for the possibility of clustering of outcomes from parent-child dyads who received the intervention from the same person. For the analysis of our primary outcome (parenting behaviors as measured by PARYC score at the first 6-month follow-up), a fixed effect for trial arm (FCU-DHH vs. TAU) will be the primary covariate of interest. Additional analyses for Hypotheses 1-4 will address each outcome over time (i.e., PARYC scores as well as continuous measures of child behavior, parent-report and objective adherence with HA/CI, and language development). To account for the correlation among repeated measurements from the same subject, in addition to random effects corresponding to the interventionists, we will also utilize an unstructured within-subject covariance structure. In these multilevel models, trial arm, time (categorical), and their interaction will be used as predictors, with the interaction being of primary interest. All tests will be two-sided with a 5% significance level and will be conducted in SAS Version 9.4 or higher (SAS Institute, Cary, NC). Furthermore, analyses will be based on intention-to-treat.

Principal components analysis and z-scores may be used to create composite language outcomes at each time-point due to the multiple measures proposed, which may reflect a single common trait. 100 Note that because rolling study enrollment is necessary (especially in smaller clinics), some parent-child dyads may have fewer observations than others.

We will measure potentially important predictors (e.g., sex, race, parental age, socioeconomic status, degree of hearing impairment, type of hearing rehabilitation device, baseline language development), and statistically compare the balance of the two trial arms. Secondary analyses will include these variables as covariates within the previously described models.

Prior to analyses, we will inspect variable distributions using histograms, probability plots, and residual plots. If necessary, transformations will be performed to make the variable distributions approximate a normal distribution. Alternatively, generalized estimating equations (GEE) may be utilized.

Missing data will be examined to determine the appropriateness of results. We will statistically summarize and compare baseline demographics from subjects who dropped out of the study relative to subjects who did not drop out, and we will look at missing data patterns (e.g., differential dropout). Afterward, using results from these analyses, sensitivity analyses may be conducted following guidelines prescribed by a National Research Council (NRC) report and described in, for example, . Multiple imputation and/or inverse probability weighting may be utilized as necessary.

(2) Procedures for students scoring the BIT speech intelligibility instrument: A private room on the UK campus (e.g., a reserved room at Young Library, an office space or classroom reserved by a member of the Study Personnel) will be used to conduct the informed consent process and the listening exercise with students who volunteer to participate. Upon arrival, the student will complete the informed consent process with the study team member, then the student will be handed a paper scoring document and an iPad with headphones. Sets of 40 audio clips (10 audio clips per child for 4 different children) will be downloaded onto the iPads, as well as 2 practice clips. All audio clips will be identified only by the child's assigned study ID number; no part of any file name or the content of the file will be identifiable. The paper scoring document will be prefilled with the 4 children's study ID numbers, as well as a study ID number assigned to the student. The student's study ID number will never be connected to their name; the sole purpose in creating the student study ID numbers is to be able to connect a student's scoring across the 4 children, in the case that the study team identifies a problem with this student's scoring (and may decide to discard scores for all 4 children). The study team member will provide instruction related to this scoring task (e.g. "listen to each audio clip only twice," "write only the words that you hear") , then the student will complete the practice items. The study team member will clarify any instructions after the practice items are completed, and then allow the student to transcribe what they hear in the 40 audio clips. This is expected to take 15-20 minutes for the student to complete, including the practice items. Study Personnel will record the UK email address for each student who completes the transcription of all 40 audio clips. A \$20 Amazon.com gift card will delivered to their UK email address within 2 weeks of their participation.

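### The stated blinding of data collectors is not protected: FCU-DHH-only satisfaction forms and session recordings may pass through the staff who later run the child and parent assessments

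*Combined protocol and SAP*

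**What the plan says.** - **Blinding.** Research Procedures, Aim 4, opening paragraph: "Research staff conducting data collection will be blinded to participants' random assignment (i.e., FCU-DHH vs. TAU". No procedure for keeping the blind is given there, and the Statistical Analysis Plan does not mention blinding.
- **Therapy Attitude Inventory (TAI).** The same section says of the 6-, 18- and 30-month follow-ups that "the FCU-DHH participants will also complete the Therapy Attitude Inventory (TAI; satisfaction measure; 5 minutes". It later repeats that the TAI "is repeated at 6-month, 18-month, and 30-month assessments".
- **Satisfaction with the interventionist (SWI).** "FCU-DHH participants will complete a 20-item set of questions that assesses their satisfaction with their interventionist", at the assessment closest to the end of their involvement. For example, "participants who enrolled in 2021 will complete these questions at their 36-month assessment", whereas 2023 enrollees answer at 18 months.
- **Mode.** Follow-up assessments are done "either online via REDCap survey, by mailed paper forms, or by telephone with trained research staff". At baseline every parent is offered telephone completion, to help with literacy or comprehension.
- **Who does what.** In the description of parent measures, the data collector conducts the MAIS interview. For the optional locator form, the data collector also puts it in the posted packet or asks for it by phone. Data collectors are trained in both the behavioral and the language measures.
- **Recordings.** Records, Privacy, and Confidentiality names data collectors as the people who capture both the parent-child task videos and the FCU-DHH session recordings used for fidelity rating. Aim 5 plans one recorded session per coach per year.

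**The concern.** A satisfaction form about a treatment, given to one arm only, discloses the arm to whoever handles it. Where a staff member posts the form or reads it out, the blinding statement cannot hold for that person and that family. A staff member who handles a family's mid-year assessment and finds no such form can infer TAU, so both arms are exposed.

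At stake are the outcomes where a staff member interacts with the family: the MAIS interview, the set-up of the recorded tasks, and the CELF, PPVT-5 and BIT given live by videoconference. Pacing, prompting and encouragement can shift with knowledge of the arm. Language development is Hypothesis 4 of the trial. PARYC or CBCL items read out by telephone are also exposed.

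**Working it through.** No calculation applies; the check sets the provisions side by side.

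**1. Can the forms reach blinded staff?** The TAI and SWI sit inside the assessments. Those assessments allow postal and telephone completion. No section exempts the two forms from these routes, assigns them to other staff, or places them after the outcomes. So yes, for families not completing online.

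**2. Does disclosure come before staff-administered outcomes?**

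| Assessment | Arm-only form | Staff-administered outcomes at that visit | Next such outcomes |
|---|---|---|---|
| 6 months | TAI | none | 12 months |
| 18 months | TAI (and SWI for 2023 enrollees) | none | 24 months, if followed that long |
| 30 months | TAI | none | 36 months |
| 36 months | SWI for 2021 enrollees | MAIS, recorded tasks, language tests | none |

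Across visits the order is certain. A family followed to 36 months has three TAI occasions, each six months before a set of staff-administered outcomes. A family ending at 18 months has one, the 6-month TAI before the 12-month assessment; its 18-month TAI and SWI precede no such outcome. Within a visit, the order of instruments is not given. At 6 months (TAI and a telephone PARYC) and at 36 months (SWI and language tests), prior disclosure is therefore possible but not shown.

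**3. Are the two groups of staff kept apart?** The text speaks of trained research staff and data collectors, with overlapping tasks. It does not say that one individual serves a family throughout, and it does not rule this out.

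**4. Is there a route independent of the forms?** Yes: session recordings. With 10 coaches planned and one recorded session each per year, this is about 10 × 1 = 10 sessions a year. It is a small route, but it conflicts with the blinding statement however families complete their questionnaires.

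**5. How many families?** The forms go to the FCU-DHH arm, planned at 72 of 125 dyads. The shares using post or telephone are not given, so the affected number cannot be derived.

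**The case against.** The strongest reply is that the exposure may be small and mostly harmless.

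- Online REDCap completion is listed first and need not reveal the arm, and staff access to REDCap data is limited to what each role needs. This stands.
- The TAI never shares a visit with the MAIS, the recorded tasks or the language tests. Any effect has to carry over six months and requires the same, or an informed, staff member. This stands; it makes the risk conditional but does not remove it.
- The MAIS is recorded and scored independently, language tests are recorded to assist scoring, two observers code the task videos, and students who see only ID numbers transcribe the BIT. This limits scoring bias, although blinding of the MAIS, task and language scorers is not separately stated. It does not address how the measures are administered.
- The primary outcome, PARYC at 6 months, is reported by parents who were told their next steps according to their arm. Assessor blinding cannot protect that, so the point bears mainly on secondary outcomes. This stands.
- Form M and the data collection checklist are attachments outside the public text and may say who gives the TAI and when. They could settle the matter, but the protocol text would still need reconciling.

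A reader might go further and infer that blinding failed for all 72 FCU-DHH families, that the person who read out the TAI also tested the child, or that the bias has a known direction. The documents support none of these. The modes used are not reported, staff continuity is not described, and because presence or absence of the form can reveal either arm, nothing fixes a direction.

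**Conclusion.** The concern holds in limited form. As written, the plan does not deliver the blinding it states: arm-only forms can be handled by research staff, data collectors are assigned FCU-DHH session recordings, and no visible provision keeps either away from later assessors. This is a conflict between provisions and not merely missing detail.

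Its size is unknown. It depends on the share of families using post or telephone, on whether the same individuals (or colleagues they inform) later assess those families, and on instrument order at the 6- and 36-month visits. The likely consequence is possible bias in administering the MAIS, the recorded tasks and the language tests, and any PARYC or CBCL items read out by telephone. It does not, by itself, undermine the primary analysis. It should be corrected in the plan and disclosed in the report.

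**What to change.** 1. **Reconcile the text.** Bring the blinding statement, the follow-up modes, the TAI and SWI provisions and the recording provision into agreement. State who was blinded, including the scorers of the MAIS, task videos and language tests, and how unblinding is recorded.
2. **Any remaining visits.** Send the TAI and SWI by a separate self-completed REDCap link after that visit's outcome forms are locked. For phone and paper families, use existing research staff who neither assess that family nor deliver or supervise its intervention; coaches and their supervisor should not collect ratings of the coach. Have sessions recorded by someone other than the family's assessor.
3. **Visits already done.** These are probably most of them, since the protocol gives May 2025 as the end of funding and lists files dated September 2025. Flag families whose TAI or SWI was handled by staff, or whose sessions a data collector captured. Add a sensitivity analysis of the MAIS and language outcomes that leaves out later assessments by that same data collector. This is re-analysis only; no child is re-tested. Because the flag can arise only in the FCU-DHH arm, apply a parallel rule to TAU families whose mid-year assessment was handled by the same person, so that the exclusion is not one-sided.
4. **Reporting.** Do not describe data collectors as blinded without this qualification.

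The cost is a separate link for two forms, a few rerouted calls, slightly lower TAI and SWI completion, and a little more analysis work.
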